**Analytic Plans**

Each study has a distinct analytic plan to address the unique specific aims of that study.

**Motivation Study**

*Primary Aim 1: Determining the main and interactive effects of the intervention components on primary outcomes.* Our primary outcomes, assessed at both 6 months (end of treatment) and 12 months, are: 1) making a serious quit attempt (defined as  $\geq 48$  hours of nonsmoking as part of an intentional effort to quit); and 2) cessation success (defined as 7-day point-prevalence abstinence (PPA)—self-reported abstinence from smoking, even a single puff). With each of the components, we hypothesize that the "on" condition will produce higher quit attempts and cessation success than the "off" condition. Data for these aims come from phone assessments over the 12 months. We will model abstinence longitudinally via a mixed-effects logistic regression model including the main effects of treatment. Longitudinal models will include the effects of time, condition, and a random subject effect to account for the correlation of repeated assessments within subjects. We will also identify any interaction effects that emerge from the combinations of intervention components. For example, we will examine whether the combination of the BR and 5Rs has a larger or smaller effect than their additive

“Breaking Addiction to Tobacco for Health (BREATHE) Study”

PI: [name], MPH, MBA; UW-CTRI Center Grant: 1P01CA180945-01.

effects would predict. Although we will examine all possible interactions of the intervention components, we do not anticipate significant effects beyond 2-way interactions. *In sum, the proposed analyses will determine whether the tested intervention components, either via main or interaction effects, increase meaningful quit attempts and long-term abstinence rates.* In addition, we will use logistic regression analyses with effects-coding to examine the effect of each intervention component on the occurrence of the binary outcomes of quit attempt occurrence and PPA at different follow-up points. Models will include only main effects and two-way interactions; no higher-order interactions are expected. Following the intent-to-treat principle, all 512 participants randomized to treatment will be included; missingness will be investigated in other analysis

*Secondary Aim 1: Determining the main and interactive effects on secondary outcomes.* We will use generalized linear mixed models to test main and interactive effects of components on smoking reduction. Entry into Cost-Optimized cessation treatment will be analyzed via logistic regression models that include main effects and two-way interactions. Cost for each treatment component will be tracked and used to identify optimal intervention components for further study and to aid decision making.

*Secondary Aim 2: Mediation analyses.* We will use a Bayesian multi-mediator approach, with the longitudinal data collected during the automated phone assessments to examine whether quit attempts and cessation success are predicted by treatment effects on key putative mediators: craving, self-efficacy, number of cigarettes smoked per day, tobacco dependence, intrinsic motivation, anhedonia, medication use, and contextual restrictions of smoking. Multi-mediator models will comprise mediators that are significant in univariate mediation analyses and allow us to address questions such as whether BR Counseling, relative to no BR, increases strength of participants’ self-efficacy, their use of reduction skills, or their magnitude of smoking reduction, and whether these increases result in increased quit attempts, and/or cessation rates. Or, does assignment to the Nicotine Mini-Lozenge condition, relative to assignment to No Nicotine Mini-Lozenge, increase participants’ self-efficacy, or decrease their craving, or amount of smoking reduction, and do these changes result in increased quit attempts, and/or cessation rates?

*Secondary Aim 3: Moderation analyses.* Potential moderators (e.g., age, gender, dependence) will be tested in moderated logistic regression models. These models will include main effects for all treatments and the moderator (e.g., gender) as well as two-way interactions of each treatment effect and the moderator.

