**Inclusion/Exclusion**

Inclusion criteria for all 3 studies will be: age (18 years or older); smoking >4 cigarettes/day for the previous 6 months; able to read, write, and speak English; have reliable phone access and agree to respond to Interactive Voice Response (IVR) phone prompts; a patient at a clinic currently recruiting in the study; not currently taking bupropion; if currently using nicotine replacement therapy (NRT) or varenicline, agreeing to use only study medication for the duration of the study; free of medical contraindications to using NRT; no history of stroke, mini-stroke, heart attack, TIA (Transient Ischemic Attack) nor an abnormal electrocardiogram in the past 4 weeks; no hospitalizations for diabetes or congestive heart failure in the past 4 weeks; no diagnosis of or treatment for schizophrenia, a psychotic disorder or bipolar disorder in the last 10 years; and, if the participant is a woman of childbearing potential, using an approved method of birth control during treatment. We will not exclude participants based on their prior use of cessation medication or if they use multiple tobacco products in order to enhance real-world generalization (these will be statistically controlled in analyses). However, we will encourage participants to discontinue use of all tobacco products on their target quit date.

Additional inclusion criteria for the individual studies include:

- Motivation Study: not currently attempting to quit smoking; not intending to quit smoking (defined as no plans to quit in the next month); and planning to remain in the area for at least 12 months.
- Cessation Study: reporting being motivated to quit; and planning to remain in the area for at least 12 months.
- Long-term Quitting Study: reporting being motivated to quit; and planning to remain in the area for at least 2 years and 2 months.

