Part of the synergy of this research arises from the use of consistent assessments across all three research studies. This consistency will allow us to compare participants and events across all three samples – including allowing us to compare smokers who are and are not motivated to quit and smokers who do and do not relapse. Assessments, which have good to excellent psychometric characteristics, will include: 1) individual difference variables related to outcome; 2) potential mediators of intervention component effects; and 3) proximal and distal outcomes. At Visit 1 participants in all 3 studies will complete a standard baseline assessment that includes: tobacco use history, demographic assessments, exhaled carbon monoxide assessment, height and weight assessment, tobacco dependence assessed via the Brief Wisconsin Inventory of Smoking Dependence Motives (WISDM-34) and the Fagerström Test of Nicotine Dependence (FTND), affect assessed using the well-validated Positive and Negative Affect Scale (PANAS), withdrawal assessed using the Wisconsin Smoking Withdrawal Scale (WSWS), and motivation and self-efficacy assessed using Likert scale items used in previous research. Participants will also evaluate the treatment provided in terms of burden and acceptability as well as their perceptions of the healthcare system for providing such treatment, using measures developed for this study based on previous research on patient satisfaction assessments. Specifically, we will assess constructs such as satisfaction with study staff, clinic staff for referring the smoker to the study, and the healthcare system for providing the treatment. Consistent mediators assessed across the 3 projects include motivation, self-efficacy, and withdrawal. There will also be study-specific baseline and follow-up assessments, as described below.

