## PROTOCOL

### “Breaking Addiction to Tobacco for Health (BREATHE) Study”

PI: [name], MPH, MBA; UW-CTRI Center Grant: 1P01CA180945-01.

a Decisional Balance Questionnaire about smoking, assessments about whether they have been encouraged to quit, and assessments of recent quit attempts and plans for future quitting. Participants will complete 4 assessment calls at Weeks 12, 26, 39 and 52 (see Table 11). Only selected items from the above scales will be used for the subsequent assessment calls. Medication usage and side effects will be assessed at every study contact for participants using Nicotine Mini-Lozenge. NRT use and smoking will be assessed at each contact using the timeline follow back procedures.

**Intensive Longitudinal Data (ILD).** Participants will receive 11 brief, automated assessment calls over 52 weeks after Visit 1 (see Table 3 for schedule). The assessment schedule will continue even if a participant receives the cessation treatment to permit standardized assessments for all participants. The 3-4 min calls will occur shortly before bedtime, based on participants’ self-reported sleep times. This has resulted in acceptable call times in our previous research. The calls will assess: withdrawal symptoms (selected items from the Wisconsin Smoking Withdrawal Scale, including craving); positive and negative affect assessed via items from the PANAS; time to first cigarette in the morning; any smoking and use during the day of the call and during the preceding 7 day period; alcohol use, quit attempts and plans for quitting; pleasure from events; medication use; intrinsic motivation to quit or reduce smoking; and self-efficacy. Missed or deferred calls will be reinitiated in 15-minute intervals. Eligible participants must have access to a phone (either cell or land line). This assessment burden is much less than has been used successfully in many other studies, and research has shown that ILD/ecological momentary assessment produces modest assessment reactivity. Our prior experience shows that IVR systems yield high quality information with response rates exceeding 80%, even among primary care patients.

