**Table 11. Schedule of Motivation Study Assessments**

Assessments	V1	Call Wk 12	Call Wk 26	Call Wk 39	Call Wk 52
Sign informed consent and HIPAA	X				
Demographics	X				
Tobacco use history	X				
Tobacco dependence	X				
Medication beliefs	X				
Height, weight	X				
Carbon Monoxide	X				
Tobacco dependence	X	X	X	X	X
Current tobacco use	X	X	X	X	X
Current alcohol use	X	X	X	X	X
Motivation, self-efficacy, and confidence	X	X	X	X	X
Dual Use		X	X	X	X

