For smoking reduction, we conducted longitudinal power analyses. We calculated statistical power for a longitudinal mixed effects regression model for the smoking reduction outcome with two groups using the RMASS2 sample size program. We specified the following parameters for the program:  $\alpha=.05$ , two-tailed test, 6 time-points (months 1, 2, 3, 4, 6, and 12), attrition of 10% at each successive time-point (a high rate), within-subject correlation=0.6, a mean difference of 1.5 cigarettes (consistent across time), and a standard deviation of 7 (consistent across time). With attrition of 10% at each successive time-point, the retention rate decreased to 59% by the 12 month follow-up. These specifications yielded a composite effect size of .27 adjusted for attrition. With a sample size of 256 per group and adjustment for attrition, we have power of at least .85 to detect this effect size with AR(1) within-subject covariance structure and correlation.

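### The Motivation Study smoking-reduction analysis does not say that Visit 1 cigarettes per day enters the model; stating it would gain precision at no cost

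*Combined protocol and SAP*

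**What the plan says.** **Model.** Analytic Plans, Motivation Study, Secondary Aim 1 gives this outcome one sentence: "We will use generalized linear mixed models to test main and interactive effects of components on smoking reduction". No covariate is named and the outcome is not defined. The only description of longitudinal terms for this study is under Primary Aim 1, next to the abstinence model: "Longitudinal models will include the effects of time, condition, and a random subject effect".

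**Covariates.** Inclusion/Exclusion has the one adjustment statement that covers all three clinical studies, "these will be statistically controlled in analyses". It refers to earlier use of cessation medication and to use of several tobacco products, not to baseline cigarettes per day.

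**Data.** Baseline smoking is available. The introduction to the data collection section says: "At Visit 1 participants in all 3 studies will complete a standard baseline assessment that includes: tobacco use history". Table 11 marks "Current tobacco use" at Visit 1 and at Weeks 12, 26, 39 and 52. The Motivation Study data collection text adds: "NRT use and smoking will be assessed at each contact using the timeline follow back procedures".

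**Power.** The Motivation Study power section treats smoking reduction separately: 256 per factor level, months 1, 2, 3, 4, 6 and 12, 10% loss at each successive time, within-subject correlation 0.6, two-sided .05, and "a mean difference of 1.5 cigarettes (consistent across time), and a standard deviation of 7 (consistent across time". It reports a composite effect size of .27 and power of at least .85 under AR(1). No baseline term is among the inputs.

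**The concern.** If how much a person smokes at entry is correlated with how much they smoke later, a model without it leaves that between-person variation in the error term. The component effects, and the interactions that the same sentence promises to test, are then estimated less precisely than the collected data allow. Chance differences in baseline smoking between factor levels also stay in the estimate.

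The silence leaves three analyses open: follow-up score only, change from baseline, and follow-up adjusted for baseline. They differ materially in power, so the choice should be fixed before the data are seen.

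**Working it through.** **Inputs from the power section:** n = 256 per level; difference d = 1.5; SD = 7 (variance 49); correlation 0.6; six times; retention 0.9^(t−1), which is 0.59 at the sixth; two-sided .05 (critical value 1.960).

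**Step 1. Reproduce the plan's figure (AR(1), no baseline term).** Average the group difference over the six times with equal weights:

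SE² = 2 × 49 × f / 256, where f = (1/36) Σ_i Σ_j 0.6^|i−j| / √(0.9^(i−1) × 0.9^(j−1)).

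- f = 0.616, so SE² = 98 × 0.616 / 256 = 0.2358 and SE = 0.4856.
- z = 1.5 / 0.4856 = 3.089, so power = Φ(3.089 − 1.960) = 0.871.
- Composite effect size = 3.089 × √(2/256) = 0.273.

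The plan states .27 and at least .85, so its figures reproduce without baseline.

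**Step 2. Add baseline to the same calculation.** Treat Visit 1 as the preceding point of the same AR(1) series with SD 7, so its correlation with follow-up t is 0.6^t. Conditioning on baseline subtracts from f the quantity (1/36)[Σ_t 0.6^t / 0.9^((t−1)/2)]².

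- The sum is 0.6 × (1 + x + … + x⁵) with x = 0.6/√0.9, so x² = 0.4 and x = 0.6325. This equals 0.6 × (1 − 0.064)/(1 − 0.6325) = 1.528.
- 1.528² / 36 = 0.065, so f falls to 0.551.
- SE² = 98 × 0.551 / 256 = 0.211, SE = 0.459, z = 3.266, power = Φ(1.306) = 0.904.
- Variance ratio, unadjusted to adjusted: 0.616 / 0.551 = 1.12.

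**Step 3. Generalised least squares (GLS) over the dropout patterns.** Information is summed over monotone dropout patterns, and SE² = 98 × f / 256 as before. Baseline again has SD 7. Its correlation with follow-up t is 0.6^t under AR(1) and 0.6 throughout under compound symmetry, the structure that a random subject effect alone implies.

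| Structure | Analysis | f | Power |
|---|---|---|---|
| AR(1) | follow-up only | 0.520 | 0.92 |
| AR(1) | change score | 0.729 | 0.81 |
| AR(1) | baseline-adjusted | 0.403 | 0.97 |
| Compound symmetry | follow-up only | 0.710 | 0.82 |
| Compound symmetry | change score | 0.506 | 0.93 |
| Compound symmetry | baseline-adjusted | 0.342 | 0.99 |

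Variance ratios, follow-up only to adjusted: 0.520 / 0.403 = 1.29 and 0.710 / 0.342 = 2.08. On the four scheduled assessment calls, with 10% loss between calls, adjusting takes power from 0.87 to 0.95 (AR(1)) and from 0.81 to 0.98 (compound symmetry).

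**Step 4. Vary the assumed baseline correlation.**

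- Compound symmetry, GLS, with a constant baseline correlation of 0.2, 0.3, 0.4 or 0.5: adjusted power 0.84, 0.87, 0.91 or 0.95, against 0.82 unadjusted.
- AR(1), time-averaged, with baseline correlation starting at 0.3 and decaying by 0.6 per step: the sum in Step 2 halves to 0.764, so f = 0.616 − 0.764²/36 = 0.600, SE = 0.479, z = 3.130 and power = 0.88, against 0.87.

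**Step 5. If SD 7 is already the SD of change.** The change-score variance is 2σ²(1 − r) and the adjusted variance is σ²(1 − r²), so their ratio is (1 + r)/2. At r = 0.6 this is 0.80, and the SD falls from 7 to 6.26. Under compound symmetry by GLS, power goes from 0.86 to 0.96.

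**The case against.** **Silence is not exclusion.** The Secondary Aim 1 sentence names effects to be tested, not a closed list of terms. The sentence on longitudinal terms sits under Primary Aim 1, beside the abstinence model. A reader might infer that the plan rejects baseline adjustment, but the documents only fail to state it. Smoking reduction most naturally means relative to baseline, and since Table 11 has smoking at Visit 1 and at every call, Visit 1 could enter as the time-zero response. With a common baseline mean, that recovers essentially the same efficiency. A power calculation without baseline does not bind the analysis. All of this stands.

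**The size depends on the method and on an input that the plan does not give.** The 0.6 describes the six post-baseline times. The entry threshold of more than 4 cigarettes per day and the 10–18% abstinence assumed in the power section could weaken the link to baseline. A reader might take the compound-symmetry gain of 17 points as the loss under this plan, but the calculation that matches the plan's .27 gives about 3 points. The figures are also normal-theory, and a count model would give somewhat different ones. This stands too, and it is why a range is reported.

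**The consequence is limited.** This is a secondary outcome in what Study Design calls a screening study. A reader might infer bias or an underpowered outcome. Neither follows: randomisation keeps the unadjusted comparison unbiased, its standard error already reflects chance imbalance, and the stated AR(1) power reproduces.

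**A change score is not always worse.** Under compound symmetry at 0.6 it beats follow-up only (0.93 against 0.82). Under AR(1), the structure behind the stated power, it does worse (0.81 against 0.92). The objection defeats a blanket statement against change scores, but not the preference for adjustment, which did better than both in every case computed.

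**Conclusion.** The point holds as a free improvement in precision. The plan does not say that Visit 1 cigarettes per day enters the smoking-reduction analysis, although everyone provides it.

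With the plan's 0.6 carried over to baseline, the gain runs from about 3 points of power (the calculation that matches the plan's effect size) through 5 points (AR(1) by GLS) to 17 points (compound symmetry by GLS). It shrinks towards nothing as the baseline correlation falls. Besides that carried-over correlation, the range assumes a baseline SD of 7, a constant treatment difference, and the plan's dropout pattern.

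The documents support no claim of bias, of an inflated error rate, or of a shortfall against the stated .85.

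**What to change.** In Analytic Plans, Motivation Study, Secondary Aim 1:

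- Define the outcome as cigarettes per day at the follow-up assessment calls.
- Include Visit 1 cigarettes per day as a fixed covariate, with the planned component coding. An equivalent model that takes Visit 1 as a response with a common baseline mean would also do.
- Prefer this to an unadjusted follow-up score or a simple change score.
- In the power section, keep the stated .85 and label it as the unadjusted figure.

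The cost is a sentence or two in the plan and one model term. No new data, contacts or participants are needed.

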**Cessation Study**

*Primary Aim 1:* A primary aim of Project 3 is to compare Abstinence-Optimized Cessation Treatment (AOCT) with Modern Usual Care (M-UC) on 7-day point-prevalence abstinence evaluated at 8, 16, 26, 39 and 52 weeks postquit. We will use GLMM implemented via SAS PROC GLIMMIX (SAS Institute Inc., Cary, North Carolina) to test the group effects in longitudinal models. Specifically, we hypothesize that participants receiving AOCT will have higher cessation rates at each timepoint than those receiving M-UC. We will also analyze other clinical outcomes because they provide complementary information about outcome (e.g., initial cessation, 6- and 12- month point-prevalence abstinence, latency to lapse and relapse, and treatment engagement and adherence) as recommended by SRNT Workgroup and others. We will evaluate initial cessation (did or did not establish 24 hours of abstinence in the first 2 weeks

“Breaking Addiction to Tobacco for Health (BREATHE) Study”

PI: [name], MPH, MBA; UW-CTRI Center Grant: 1P01CA180945-01.

following the quit day) and 6- and 12-month abstinence rates using logistic regression and latency to lapse and relapse using Cox proportional-hazards regression. We will also examine cessation outcomes controlling for treatment adherence in secondary analyses. The distributions of the adherence data (percentage of days using nicotine replacement; number of mini-lozenges used per day; percentage of counseling sessions completed) will be examined to inform decisions about transformation and analysis options.

*Primary Aim 2:* Another primary aim is to compare AOCT and M-UC on outcomes important to healthcare systems: net monetary benefit (NMB), incremental cost-effectiveness ratio (ICER), cost per long-term quit, and patient ratings of treatment and healthcare system quality. All of these will inform decision-making with regard to the efficient allocation of healthcare resources. Specifically, we hypothesize that, relative to M-UC, AOCT will produce an NMB higher than zero. Net monetary benefit analyses will convert the long-term relapse rates to Quality-Adjusted Life Years added (QALYs) and then monetize the QALYs added using a range of willingness to pay values. NMB analyses will allow us to compute confidence intervals and report whether these confidence intervals overlap for the AOCT relative to M-UC. For the ICER analyses, we will compare the additional cost of the AOCT to M-UC costs. Participants’ quality ratings will be analyzed using ANOVAs. We will examine the role of cessation success in satisfaction ratings and control for cessation success as needed.

*Secondary Aim:* The secondary aim is to understand better the underlying treatment mechanisms of the Abstinence-Optimized Cessation and Modern Usual Care treatments and to determine which effects mediate cessation success. We will use mediational models similar to those used in our previous research to estimate the extent to which treatment-related change in the mediator (e.g., change in self-efficacy, craving, negative affect, or perceived support) leads to improved outcomes (initial cessation, latency to relapse). The EMA data on daily urges, smoking, treatment-related support, withdrawal, cue exposure, coping, etc. will be combined with the other phone assessments and studied using latent growth curve models. For example, we will examine whether AOCT’s use of a Combination NRT component results in greater withdrawal suppression and thereby reduced likelihood of relapse, relative to the M-UC treatment and whether the counseling in the optimized treatment produces greater intratreatment social support and coping skills and thereby reduces the likelihood of relapse relative to M-UC treatment. We will use procedures from our prior work to reduce error and ensure temporal ordering of causal modeling. Parameters of the growth models (e.g., intercept and trajectory parameters) will be studied as mediators of short-term outcomes such as initial cessation and lapse or relapse. We will also examine orthogonal mediation paths via multiple mediator analyses. Mediational analyses will be conducted using Mplus, which offers flexibility in the handling of outcome variables (e.g., continuous, categorical counts, censoring).

We will also conduct exploratory analyses to determine whether individual difference variables such as gender, race, educational attainment, and baseline nicotine dependence moderate treatment effects using chi-square analyses and by modeling interaction effects in Cox Regression. We will also examine moderated mediation to determine whether any of these individual difference variables moderate specific treatment effects.

“Breaking Addiction to Tobacco for Health (BREATHE) Study”

PI: [name], MPH, MBA; UW-CTRI Center Grant: 1P01CA180945-01.

